### Study Protocol:

Following study enrolment (visit 1), each subject underwent a 75-g oral glucose tolerance test (OGTT). Participants who met the eligibility criteria were then continuously monitored for 72 hours (visit 2 to visit 3) with a retrospective continuous glucose monitoring (CGM) system (Medtronic, Northridge, CA). After 3 days of CGM (visit 3), the subjects were randomized (1:1) to receive either study group or control group for 4 weeks. Participants in the study group were instructed to replace breakfast with Glucerna SR (Abbot Nutrition) powder 52 g dissolved in 200 ml of warm water and both groups received lifestyle education. At the end of the 4-week intervention, subjects underwent another CGM from visit 4 (Day 29) to visit 5 (Day 32), at which a final OGTT in the fasting state was conducted. The schematic outline of study conduction is illustrated in the figure below.

The incremental area under the curve of postprandial blood glucose (AUCpp) during CGM was calculated as the area between the glucose concentration-time curve, and the pre-prandial baseline glucose value measured at 4 h after each meal. Intra-day glycaemic variability (GV) parameters include the standard deviation of blood glucose values (SDBG), glucose coefficient of variation (CV), and the mean amplitude of glycaemic excursions (MAGE). CV was calculated by dividing the SDBG by the mean of the corresponding glucose readings. MAGE was calculated as the arithmetic mean of the differences between consecutive peaks and nadirs. Only excursions of more than

1 SDBG of the mean glycaemic values were considered for the calculation of MAGE.

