Anthropometric and biochemical parameters were measured at visit 1 (baseline) and visit 4 (post-intervention). Body mass index (BMI) was calculated as the weight (kg) divided by squared height (m). Blood pressure (BP) was measured twice using a standard mercury sphygmomanometer, and the average was documented. Venous blood samples were collected after an overnight fast. Biochemical parameters including fasting plasma glucose (FPG), 2-h plasma glucose (2h-PG) during OGTT, glycated haemoglobin A1c (HbA1c), glycated albumin (GA), insulin, triglycerides (TG), total cholesterol (TC), high density lipoprotein cholesterol (HDL-C), and low-density lipoprotein cholesterol (LDL-C) were assayed. Insulin sensitivity was evaluated by homeostasis model assessments of insulin resistance (HOMA-IR):  $\text{HOMA-IR} = \text{fasting insulin (in mU/L)} \times \text{FPG (in mmol/L)} / 22.5$ .

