### **Statistical analyses**

Continuous variables at baseline were compared between the two groups by Student's *t* test. Comparison of categorical variables between groups was performed by  $\chi^2$  tests. Differences in the parameters before and after treatment were analysed by paired *t* test. The changes ( $\Delta$ ) in variables were compared with Student's *t* test. Statistical analyses were performed using SPSS software version 17.0 (SPSS Inc., Chicago, IL, USA). A *P* value of  $< 0.05$  (two-tailed) was considered statistically significant.

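### Changes in insulin, HOMA-IR and triglycerides are tested without baseline adjustment or a named transformation; the test is valid but probably loses power if these markers are skewed and the effect is proportional

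*Combined protocol and SAP*

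**What the plan says.** The Statistical analyses section gives three rules for continuous data.

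- At baseline: "Continuous variables at baseline were compared between the two groups by Student's *t* test".
- Within group: "Differences in the parameters before and after treatment were analysed by paired *t* test".
- Between groups: changes "in variables were compared with Student's *t* test".

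Significance is P < 0.05 ("two-tailed) was considered statistically significant"). The section names no log transformation, percent change, rank-based test or covariate.

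The Study Protocol section puts the markers in question under these rules. The assay list includes "insulin, triglycerides (TG), total cholesterol (TC), high density lipoprotein cholesterol (HDL-C", and "Insulin sensitivity was evaluated by homeostasis model assessments of insulin resistance (HOMA-IR", computed as fasting insulin times FPG divided by 22.5. Biochemical parameters are measured at visit 1 and again at visit 4, so a baseline value is planned for each. Allocation is 1:1.

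The documents do not say in words that changes are taken on the raw scale. That is inferred from a change score with no transformation named.

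**The concern.** Insulin, triglycerides and an index built from insulin are positive quantities that may well be right-skewed. If treatment lowers such a marker by a percentage, the absolute change is larger in subjects who start high. Those subjects then supply more than their share of the variance of the change, and the standard error of the mean difference grows. The change score also fixes the coefficient of the baseline value at 1. When the pre/post correlation is well below 1, that adds noise which a baseline covariate would remove.

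The risk is that a real proportional fall in insulin resistance or triglycerides is missed or estimated imprecisely, and that the mean change leans on the subjects with the highest values.

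**Working it through.** **Inputs from the documents:** Student's t test on change; two-sided alpha 0.05; 1:1 allocation; HOMA-IR = insulin × FPG / 22.5. The documents give no sample size, power or effect size, so there is no figure of the plan's own to reproduce.

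**Assumed inputs:** log-normal marker; 20% proportional reduction (ratio 0.8); 50 per arm; log-SD s = 0.6; log-scale pre/post correlation ρ = 0.5 or 0.7. A log-SD of 0.6 is a CV of √(exp(0.36) − 1) = 0.66.

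**Step 1. Approximate power, Φ(effect/SE − 1.96).** On the log scale the effect is −ln 0.8 = 0.2231. On the raw scale, in units of the baseline mean, it is 0.20.

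- Log change: SD = 0.6 × √(2(1 − ρ)) = 0.600 or 0.465. SE = SD × √(2/50) = 0.120 or 0.093. Power is about 46% or 67%.
- Log ANCOVA: SD = 0.6 × √(1 − ρ²) = 0.520 or 0.428. SE = 0.104 or 0.086. Power is about 57% or 74%.
- Raw change: let k = exp(0.36ρ) − 1 = 0.197 or 0.287. Control variance = 2(0.4333 − k) = 0.472 or 0.293. Treated variance = 1.64 × 0.4333 − 1.6k = 0.395 or 0.252. SE = √(sum/50) = 0.132 or 0.104. Power is about 33% or 48%.

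**Step 2. Simulated power, same inputs.**

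| Analysis | ρ = 0.5 | ρ = 0.7 |
|---|---|---|
| Raw change, t test | 32% | 51% |
| Log change, t test | 45% | 68% |
| Raw ANCOVA | 47% | 64% |
| Log ANCOVA | 56% | 75% |

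The three rows that have a formula in Step 1 agree with it within about 3 points.

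**Step 3. Source of the gain.** From raw change to log ANCOVA the gain is 24 points at both correlations (56 − 32; 75 − 51).

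- Adjusting first gives 47 − 32 = 15 points (63%) or 64 − 51 = 13 points (54%).
- Taking logs first leaves 56 − 45 = 11 points (46%) or 75 − 68 = 7 points (29%) for adjustment.

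The split depends on the order and on the inputs. At 60 per arm, CV 1.0 and ρ = 0.8 (raw change 38%, raw ANCOVA 46%, log ANCOVA 69%), adjustment entered first gives only 8 of 31 points.

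**Step 4. Sensitivity to spread** (20% reduction; 30 to 100 per arm; ρ = 0.6 or 0.8).

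| CV | Power lost, raw change v. log change | Share of the within-arm sum of squares of change from the top 10% by baseline |
|---|---|---|
| 0.3 | 0-7 points | 22-25% |
| 0.5 | 1-14 points | 30-33% |
| 0.7 | 10-19 points | 35-42% |
| 1.0 | 8-28 points | 41-52% |

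**Step 5. Type I error.** With no effect, on the Step 4 grid, the raw-change test rejected in 4.1% to 5.4% of trials. A separate run at 30 per arm and log-SD 0.8 gave 3.6%, which is slightly conservative.

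**Step 6. Other data models, 50 per arm.**

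- Log-normal baseline (log-SD 0.6) with additive error and an additive shift: raw change 72% v. log change 53%; raw ANCOVA 72% v. log ANCOVA 55%. A second run of this type gave 80% v. 57% for raw and log change.
- Normal data, CV 0.35, additive shift: raw change 62% v. log change 56%.
- Constant absolute reduction of 20% of the mean on log-normal data (log-SD 0.4, values floored just above zero): raw change 65-85% v. log change 87-98%. The floor may favour the log analysis here.

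The ranking in Step 2 therefore belongs to its model and can reverse.

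**The case against.** The strongest reply is that the harm is assumed. A log-normal marker with a proportional effect is the setting that suits a log analysis best, so the ranking is largely built in. The documents offer no data on skewness or on the form of the effect. This stands: the loss must be stated conditionally, and Step 6 shows that the log scale costs power when error and effect are additive.

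Several stronger readings are tempting, and the documents do not support them.

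- *The t test is invalid.* It is not. Under 1:1 randomisation it holds its level and estimates an interpretable absolute mean difference.
- *A handful of subjects dominates the result.* Disproportionate weight is as far as one can go. The top tenth by baseline approaches half of the sum of squares only near CV 1.0.
- *The HOMA-IR formula proves multiplicative behaviour.* A product is additive on the log scale, but that does not show that treatment acts proportionally or that errors are multiplicative. It also says nothing about insulin or triglycerides, which are assayed directly.
- *The raw scale is the whole cause.* Step 3 shows that missing baseline adjustment accounts for a substantial part. Scale still matters by itself: under the proportional model, log change beats raw change and log ANCOVA beats raw ANCOVA.
- *The trial's main question is at risk.* The documents do not name these markers as primary, and much of the design concerns CGM measures.

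**Conclusion.** The point holds in conditional form. The plan states a method for insulin, HOMA-IR and triglycerides that uses neither the baseline value as a covariate nor, as far as the text shows, a transformation. If the markers are right-skewed and the effect is proportional, moving to log ANCOVA raises power by about 24 points at 50 per arm, log-SD 0.6 and correlation 0.5 to 0.7. The scale change alone gives 45 − 32 = 13 or 68 − 51 = 17 points. At low spread, or where power is already near 100%, the loss is small. Under purely additive error and effect, the log scale is the worse choice.

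No false-positive problem follows. This is a moderate improvement to three markers not designated as primary, held with medium confidence because sample size, spread, correlation and form of effect are all assumed.

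**What to change.** In the Statistical analyses section, replace the t test on change for these three markers with wording such as:

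> For fasting insulin, HOMA-IR and triglycerides, groups are compared by ANCOVA of log(post-intervention value) on group and log(baseline value). The result is reported as the ratio of geometric means with 95% CI. A baseline-adjusted analysis on the raw scale is given as a sensitivity analysis.

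Name the markers in advance and do not let a normality test choose the scale. If the within-group paired comparison is kept for these markers, use the same scale.

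The cost is a few lines of text and a log transform, with no new data. The downsides are that the main result becomes a ratio instead of an absolute difference, and that power is lower if effects are in fact additive; the raw-scale sensitivity analysis covers both. If the analyses are already complete, the re-analysis should be labelled post hoc.

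### One P < 0.05 rule covers between-arm tests of change in 16 to 19 outcomes, with no primary outcome, testing order, multiplicity control or exploratory label in the available text

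*Combined protocol and SAP*

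**What the plan says.** The Statistical analyses section says that the changes "in variables were compared with Student's" t test, without restricting which variables are meant. It also gives paired t tests of before against after. One threshold serves all of them: P below 0.05 "two-tailed) was considered statistically significant". The section is in the past tense ("Statistical analyses were performed using SPSS software version 17.0").

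The outcomes come from the Study Protocol section. The continuous glucose monitoring (CGM) measures are the incremental postprandial area (AUCpp) and the variability measures: "Intra-day glycaemic variability (GV) parameters include the standard deviation of blood glucose values (SDBG), glucose coefficient of variation (CV") and MAGE. The other measures are BMI, blood pressure, nine laboratory values (FPG, 2h-PG, HbA1c, GA, insulin, TG, TC, HDL-C, LDL-C) and HOMA-IR.

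Participants in the study arm were "instructed to replace breakfast with Glucerna SR", while "both groups received lifestyle education".

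The available text names no primary or secondary outcome and gives no testing order, multiplicity adjustment or exploratory label. It also gives no sample size.

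**The concern.** A 5% threshold limits false positives to 5% for one test chosen in advance. Here the same threshold applies to every between-arm change, and nothing in the available text says which one decides whether the product works. A reader who sees one significant result among 16 or more cannot tell whether that outcome was the target or was picked out because it was significant. If a product claim can rest on any of them, its false positive rate is that of the whole set, which is far above 5%.

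The paired tests within each arm offer no way round this. Both arms receive lifestyle education, so an improvement within one arm does not isolate the product.

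**Working it through.** The documents state no familywise error rate, power or sample size, so there is no figure of the plan's own to reproduce.

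**1. Count the outcomes (k).** From the Study Protocol section: AUCpp 1 + variability measures 3 + BMI 1 + blood pressure 1 + laboratory values 9 + HOMA-IR 1 = **16**. Testing systolic and diastolic pressure separately gives **17**. Also testing AUCpp separately for three meals gives **19**. Both splits are assumptions. Within-arm and baseline tests are not counted.

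**2. Expected false positives if the product affects nothing.** This is 0.05 × k, whatever the correlations: 0.05 × 16 = 0.80; 0.05 × 17 = 0.85; 0.05 × 19 = 0.95.

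**3. Chance of at least one, independent outcomes.** 1 − 0.95^k gives 0.560, 0.582 and 0.623. This is only an upper reference, because several outcomes are linked by construction:
- "CV was calculated by dividing the SDBG by the mean of the corresponding glucose readings".
- For MAGE, only excursions above "1 SDBG of the mean glycaemic values were considered for the calculation of MAGE".
- HOMA-IR is fasting insulin × FPG / 22.5.

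**4. Equal correlation ρ (assumed).** With c = 1.96, the chance is 1 − ∫ [Φ((c − √ρ·u)/√(1−ρ)) − Φ((−c − √ρ·u)/√(1−ρ))]^k φ(u) du, integrated numerically.

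**5. Correlation high only within related groups (assumed).** The groups are CGM; BMI; blood pressure; FPG, 2h-PG, HbA1c and GA; insulin and HOMA-IR; and lipids. For k = 17 their sizes are 4, 1, 2, 4, 2 and 4. For k = 16 the blood pressure group has 1, and for k = 19 the CGM group has 6. Each case used 2,000,000 simulated draws.

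| Assumed correlation | k = 16 | k = 17 | k = 19 |
|---|---|---|---|
| Independent | 56% | 58% | 62% |
| Equal, 0.3 | 48% | 49% | 53% |
| Equal, 0.5 | 37% | 39% | 41% |
| Equal, 0.7 | 26% | 27% | 28% |
| Equal, 0.9 | 15% | 15% | 15% |
| 0.7 within groups, 0.1 between | 45% | 47% | 49% |
| 0.9 within groups, 0.2 between | 36% | 37% | 38% |

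**6. Cross-check with t tests.** Simulated two-sample t tests at assumed sizes of 15, 30 and 60 per arm, for k = 16 and 19, gave 47.7 to 52.9% at ρ = 0.3 and 26.5 to 29.4% at ρ = 0.7. The normal approximation is adequate.

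**7. Error rate under the proposed remedy, all nulls true.** One primary at 0.05, with a three-outcome list tested by Holm only if the primary is significant, gives 0.050. Without that condition, independence gives 1 − 0.95 × (1 − 0.05/3)³ = 0.097, and simulation at ρ = 0.7 gives 0.073. The list therefore has to be conditional on the primary.

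**The case against.** The strongest objection is that part of the document was not available and no registry record was consulted, so a primary outcome may be named elsewhere. If so, its 0.05 test has a 5% error rate, and what remains is an unlabelled set of secondary outcomes, which is a smaller point. This stands as a condition on the conclusion. It does not change the Statistical analyses section, which is visible and neither reserves the threshold for one outcome nor labels the others.

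Second, the count is inferred. The plan does not say that every measured variable is an efficacy outcome, and BMI, blood pressure and lipids could be descriptive. That is fair, but the conclusion survives a much shorter list. With only the four CGM outcomes the chance is 1 − 0.95⁴ = 18.5% if independent and about 13% at correlation 0.7.

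Third, independence cannot hold and one common correlation is unrealistic. This is correct. The grouped cases, 36 to 49%, fit the structure of the outcomes better.

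Fourth, each test keeps its own 5% error, and the plan does not say that any single significant result would establish an effect. That is also true. But the plan does not say which result would, so it does not rule out that reading.

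Finally, the past tense suggests that it may be too late to name a primary before analysis. That limits the remedy but not the finding.

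**Conclusion.** The concern holds for the available text. Under the rule as written, a product with no effect on any listed outcome would still show at least one significant between-arm difference with a probability well above 5% in every case tried. The range runs from about 15% at an extreme common correlation of 0.9 to 62% for 19 independent outcomes.

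This rests on the inferred count of 16 to 19, on no true effect on any outcome, and on assumed correlations, since the documents give none. The expected 0.80 to 0.95 false positives does not depend on the correlations. Confidence is medium, because a primary outcome may be named in text that was not available. The plan should be changed, since a product claim made under this rule could be unsound.

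**What to change.** In the Statistical analyses section:

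- **Primary test.** Reserve two-sided 0.05 for one between-arm comparison. If a primary outcome is already named or registered, use that one. If there is none and outcome data have not been seen, name one before analysis. Change in post-breakfast AUCpp is a reasonable candidate because only breakfast is replaced. Its definition must be settled first, since the Study Protocol section describes a pre-meal baseline yet places its measurement 4 h after the meal.
- **Other outcomes.** Report all other between-arm changes and all within-arm comparisons as estimates with 95% confidence intervals, labelled exploratory. Base no product claim on within-arm tests.
- **Further claims, if wanted.** Name a short list in advance and test it by Holm at 0.05 only if the primary is significant.
- **If data have been seen and no primary was registered.** Label all between-arm results exploratory.

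The cost is wording only, with no extra participants or measurements. Fewer outcomes can be called significant, and none of the listed secondaries can be claimed if the primary test fails. The cost in power cannot be computed without a sample size. If the data have been seen and no primary was registered, the change is an honest label and cannot restore a confirmatory test.
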